8.6 LOCF endpoint

The last observation from Day 1 through 7 days after the final application of DSP-5423P, except for baseline data defined in section 8.4, will be carried forward and will be defined as the Week 52 (LOCF).

8.7 Missing data

Individual missing item in any scale will not be imputed. For the rating scales that consist of more than one item, if any item is missing, then the total and subscale scores will also be handled as missing. In case that any value derived in EDC and one calculated along with the SAP are different, the later will be adopted for the analysis.

Missing/partial date will be imputed according to the following rules. In the listings, the original date without any imputation will be presented. The last visit date is the last date of visit among all visits including follow-up visits and unscheduled visits.

1) Adverse event

End date should be imputed first, and then Start date will be imputed based on imputed end date.

End Date:

1. If ongoing is checked, no imputation will be performed.
2. If ongoing is not checked and end date is totally missing or year is missing, then end date will be imputed as the last visit date.
3. If only day of end date is missing, end date will be imputed as the earlier one of following dates: the last day of that month and the last visit date.
4. If both month and day (or only month) of end date is missing, end date will be imputed as the earlier one of following dates: the last day (Dec31) in that year or the last visit date.

Start Date:

1. If start date is totally missing and end date is also missing (ongoing), no imputation will be performed. For subjects applied DSP-5423P, although the events are summarized as TEAE, those are not included in summaries by the initial onset date of the event.
2. If start date is totally missing and end date is not missing, start date will be imputed as the earlier one of following dates: end date of AE or date of the initial application date of DSP-5423P.
3. If only day of start date is missing, and start date is in the same year and month of initial application date of DSP-5423P, start date will be imputed as earlier one of following non-missing dates: end date of AE or date of the initial application date of DSP-5423P.
4. If only day of start date is missing, and start date is not in the same month of initial application date of DSP-5423P, start date will be imputed as the first day in that month.
5. If both month and day (or only month) of start date is missing, and start date is in the same year of initial application date of DSP-5423P, start date will be imputed as earlier

one of following non-missing dates: end date of AE or date of the initial application date of DSP-5423P.

6. If both month and day (or only month) of start date is missing, and start date is not in the same year of initial application date of DSP-5423P, start date will be imputed as the first day (Jan01) in that year.

2) Prior/Concomitant Medication

End Date:

1. If ongoing is checked, no imputation will be performed.
2. If ongoing is not checked and end date is totally missing or year is missing, then end date will be imputed as the last visit date.
3. If only day of end date is missing, end date will be imputed as the earlier one of following dates: the last day of that month and the last visit date.
4. If both month and day (or only month) of end date is missing, end date will be imputed as the earlier one of following dates: the last day (Dec31) in that year or the last visit date.

Start Date:

1. If the medication is 'started prior to study' (checked in the CRF), no imputation will be performed (That medication should be defined as prior medication).
2. If the medication is not 'started prior to study' (checked in the CRF) and start date is totally missing, no imputation will be performed (That medication should be defined as neither prior medication nor concomitant medication).
3. If only day of start date is missing, start date will be imputed as the first day in that month.
4. If both month and day (or only month) of start date is missing, start date will be imputed as the first day (Jan01) in that year.

3) Initial/Current Episode of Schizophrenia

For the purpose of the estimation of Duration of illness and duration of current episode, the day of onset date of initial/current episode will be imputed according to the followings;

1. If onset date is totally missing, no imputation will be performed.
2. If only date of onset date is missing, onset date will be imputed as the first day in that month.
3. If only month of onset date is missing, and onset date is in the same year of informed consent, onset date will be imputed as previous day of informed consent.
4. If only month of onset date is missing, and onset date is not in the same year of informed consent, onset date will be imputed as June 30th.

9. Statistical Method

All efficacy, safety and other analysis are based on Safety Analysis Population, and PK analysis are based on PK analysis population. All subjects and data collected will be presented in listings.

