7.2 Safety endpoints

- 1) Adverse events (AEs) and adverse drug reaction (ADRs)
- 2) Extrapyramidal AEs and ADRs
- 3) Skin-related AEs and ADRs at the application site
- 4) Assessment of skin irritation reaction at the application site
- 5) Change in Drug-Induced Extrapyramidal Symptoms Scale (DIEPSS) Total Score (excluding overall severity) from baseline
- 6) Change in individual DIEPSS scores from baseline
- 7) Serum prolactin concentration
- 8) Electrocardiogram (ECG) parameters (QTc)
- 9) Concomitant use of antiparkinson drug
- 10) Assessment of suicides using Columbia-Suicide Severity Rating Scale(C-SSRS)
- 11) Laboratory test values, vital signs and body weight

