9.7 Prior and Concomitant Medications

For Cohort 1, prior medications are defined as those taken prior to initial dose of DSP-5423 (tablet). For Cohort 2, prior medications are defined as those taken prior to initial application of DSP-5423P. Prior medications will include medications that had been used before participation of the study, which are collected as “Started prior to study” on the CRF.

For Cohort 1, concomitant medications during DSP-5423 (tablet) treatment period are defined as those taken from the initial dose date of DSP-5423 (tablet) through the last dose date of DSP-5423 (tablet). For both Cohort 1 and Cohort 2, concomitant medications during DSP-5423P application period are defined as those taken from the initial application date of DSP-5423P through the last application date of DSP-5423P. Note that the concomitant and prior medications are not mutually exclusive, ie, a medication can be classified as both prior and concomitant medication.

Prior and concomitant medications will be coded using the WHO Drug Dictionary [March 1, 2014 version], Anatomical Therapeutic Chemical (ATC) Classification codes and preferred term (PT, Standardized Medication Name), and summarized for each cohort and cohort total. The number and percentage of subjects who took prior or concomitant medications will be summarized as well.

Prior and concomitant medications will be summarized as the number and percentage of subjects by ATC level and PT for each cohort. If a subjects took same medications in terms of ATC level or PT multiple times, the subject will be counted one time into associated ATC level or PT. In addition, Prior and concomitant medications will be summarized as to following categories defined on the CRF;

Antipsychotics

Antiparkinson drugs

Psychotropic drugs

Hypnotic drugs

The number and percentage of subjects with concomitant use of antiparkinson drugs will be summarized by cohorts and visits. Denominator for visit base summary will be subjects who received DSP-5423 (tablet) during relevant periods or subjects who received DSP-5423P during relevant periods. Note that denominator at Day -1 and one for overall period will be all subjects in Safety Analysis Population. Subgroup analysis for subjects who didn't use antiparkinson drugs at Day -1 will be repeated in the same fashion.

DSP-5423 (tablet) treatment period: (overall)

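### SAP 8.7 leaves an undated, non-prior medication unclassified even when its stop date shows use during a treatment period, contradicting the use-based definition in SAP 9.7

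*SAP*

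**What the plan says.** SAP 8.7, part 2) Prior/Concomitant Medication, Start Date rule 2 reads: "If the medication is not 'started prior to study' (checked in the CRF) and start date is totally missing, no imputation will be performed". The parenthesis that follows gives the consequence: "That medication should be defined as neither prior medication nor concomitant medication". The rule takes no account of the stop date.

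The neighbouring rules are more generous. A partial start date is completed: "If only day of start date is missing, start date will be imputed as the first day in that month", or to 1 January when the month is also missing. A missing end date is completed too, with the day on which the subject was last seen: "If ongoing is not checked and end date is totally missing or year is missing, then end date will be imputed as the last visit".

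SAP 9.7 sets the classes by use. For the patch period, "concomitant medications during DSP-5423P application period are defined as those taken from the initial application date of DSP-5423P"; this window closes when the final patch is applied. The tablet period in Cohort 1 is handled in the same way, and prior medication is whatever was taken before first dosing.

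SAP 7.2 lists "Concomitant use of antiparkinson drug" as safety endpoint 9, and SAP 9.7 says how it is reported: "The number and percentage of subjects with concomitant use of antiparkinson drugs will be summarized by cohorts and visits". Protocol 15.3.6.4 asks for the same count over the patch period.

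**The concern.** Two parts of the SAP give different answers for the same record. Under 9.7, a drug with a stop date in the patch period was taken in that period and is concomitant. Under 8.7 it belongs to no class. SAP 9.7 and Tables 14.1.7.1 to 14.1.7.13 present only prior and concomitant medications, with no unclassified category, so the record reaches none of these tables, nor Figure 14.3.3.3.

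The drugs most affected are the ones a safety reader looks for. Protocol 10.3.3.2 allows antiparkinson drugs during treatment only when extrapyramidal symptoms occur or worsen. Protocol 10.3.3.1 allows a rescue antipsychotic only for urgent symptoms and limits its total duration to 10 days. Safety is the primary objective, and losing confirmed use of either class makes the product look slightly better tolerated than the data show.

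**Working it through.** The plan attaches no figure to this point, so there is nothing to reproduce. The check sets the two rules side by side for a medication with the prior-to-study box unchecked and no start date.

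| Recorded stop date | Class under SAP 9.7 | Class under SAP 8.7 rule 2 |
|---|---|---|
| Before first dosing | Prior | None |
| Within the tablet period (Cohort 1) | Concomitant, tablet period | None |
| Within the patch period | Concomitant, patch period | None |
| After last application, ongoing, or missing | Not decidable from the dates | None |

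**First three rows.** The stop date alone settles a class under 9.7, and rule 2 discards it. These rows are a contradiction.

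**Last row.** Protocol 10.3 and SAP 7.2.2 collect medications up to the follow-up visit, whereas the concomitant window closes at the last application. A drug begun in follow-up is correctly outside both classes. A drug begun during treatment is wrongly left out. The dates cannot separate the two.

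**Comparison with adverse events in the same section.** When the start date is wholly missing and the event is ongoing, AE rule 1 keeps it in the main tables: "although the events are summarized as TEAE, those are not included in summaries by the initial onset date of the event". When the end date is known, AE rule 2 sets the start to the earlier of the end date and first application. An event ending on or after Day 1 is then treatment-emergent, and one ending before Day 1 is not. The AE rules therefore use the end date; medication rule 2 does not.

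**Size per omitted user.** If the undated record is the subject's only record of that drug or class, the reported percentage falls by 100/N points. The values of N below are planning figures from SAP 5, used as illustrations and not as the actual table denominators:

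- N = 50 (Cohort 1 subjects with at least 6 weeks on the patch): 100/50 = 2.0 points
- N = 100 (subjects with 52 weeks on the patch): 100/100 = 1.0 point
- N = 200 (planned enrolment): 100/200 = 0.5 point

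The number of such records is not given, so no total effect can be calculated.

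**The case against.** A reader might infer that any such drug must have begun on study, since it did not begin before, and that the rule therefore always biases use downward. The documents do not support this. Recording runs through follow-up, where Protocol Table 10 leaves antiparkinson drugs and antipsychotics unrestricted, and both classes are also recorded during washout. An unchecked box without a date may also simply be an incomplete entry. For a drug begun in follow-up, rule 2 gives the right answer and no bias.

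A reader might also infer that affected subjects vanish from every medication table. They do not if they have another dated record, because the tables count each subject once per drug or class.

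Nor does the AE section simply do the opposite. Its rule 1 covers only ongoing events, and a treatment-emergent event may start after the last application, whereas concomitant medication may not.

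Finally, such records may not exist. Start date is a CRF item, partial dates are imputed, restricted medications are also recorded at efficacy assessments (Protocol 11.2), CRFs are monitored for completeness (Protocol 16.2), and a data review precedes lock (SAP 9.3). No test or decision rule depends on these tables.

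All of this stands, and it limits the point. It does not remove the conflict where a recorded stop date proves use. The general promise in SAP 9 to list all data is only a partial safeguard: the medication listings (16.2.4.4 to 16.2.4.6) are titled prior or concomitant, so it is unclear where an unclassified record would appear.

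**Conclusion.** The point holds in a narrow form and is minor. SAP 8.7 rule 2 contradicts SAP 9.7 whenever a recorded stop date places an undated, non-prior drug inside a treatment period. The result can be an under-count of antiparkinson use and rescue antipsychotic use, at 100/N percentage points per omitted user.

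This assumes that the subject has no other dated record of the drug or class. The number of affected records is unknown and may be zero, so the documents support no range for the overall shift. For records that are ongoing, lack a stop date, or stop after the last application, the SAP is choosing a convention under real uncertainty. There the case for change rests on preferring the conservative direction in a safety table, not on a contradiction.

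**What to change.** Replace the parenthesis in SAP 8.7, part 2), Start Date rule 2 with:

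> If the recorded (non-imputed) stop date falls from the first through the last dose/application date of a treatment period, the medication is concomitant in that period. If it is ongoing, or its stop date is missing or after the last application, it is counted as concomitant in the DSP-5423P overall row only, unless other CRF data show that it started after the last application. If the stop date precedes first dosing, it is prior. These records are left out of by-week rows, and their number is footnoted.

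The stop date must be the recorded one because a missing end date is otherwise imputed to the last visit, which is no evidence of use in any period. The text also avoids counting one Cohort 1 record in both the tablet and patch periods without evidence.

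The cost is one SAP passage, a small change to the classification program, and a footnote. No new data are needed. The downside is that a few drugs begun in follow-up may be counted as patch-period use. That errs on the conservative side for safety, and the footnote makes it visible.

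### Partial medication start dates go back to the first of the month or year with no floor, so some drugs begun on treatment count as prior, tablet-phase or Day -1 use

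*SAP*

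**What the plan says.** The medication part of SAP 8.7 Missing data has four start-date rules.

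- Rule 1: "If the medication is 'started prior to study' (checked in the CRF), no imputation will be performed". The drug is classed as prior.
- Rule 2: "If the medication is not 'started prior to study' (checked in the CRF) and start date is totally missing, no imputation will be performed". The drug is classed as neither prior nor concomitant.
- Rule 3: "If only day of start date is missing, start date will be imputed as the first day in that month".
- Rule 4, month and day or month alone: "missing, start date will be imputed as the first day (Jan01) in that year".

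SAP 9.7 then classifies by date. Its Cohort 2 definition reads: "For Cohort 2, prior medications are defined as those taken prior to initial application of DSP-5423P". In Cohort 1 the boundary is the first tablet dose, and use between the first and last tablet dose is tablet-phase concomitant. A drug may be both prior and concomitant.

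SAP 9.7 also tabulates antiparkinson use at Day -1 and by week band on patch, and repeats the table in subjects without use at Day -1. Antiparkinson use is a listed safety endpoint (SAP 7.2).

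The adverse event rules in SAP 8.7 work differently. If the partial date shares the month, or with the month missing the year, of the first patch, then "start date will be imputed as earlier one of following non-missing dates: end date of AE" or the first patch date.

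**The concern.** Rule 1 removes the ticked drugs, so rules 3 and 4 operate only on drugs that the CRF does not mark as started before the study. For these, the earliest possible date can fall before the first dose, and even before screening. SAP 9.7 classifies on that date.

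The analysis most exposed is the antiparkinson summary in subjects without use at Day -1, which shows new use on the patch. A new user whose start is moved back appears to be a Day -1 user and leaves that subgroup. In Cohort 1 the same record adds spurious use to the tablet-phase table, which bears on the secondary objective of switching from tablet to patch.

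The two sets of rules can also disagree about one episode. Take an extrapyramidal event and the drug given for it, both lacking the day and both in the month of the first patch. The event is dated Day 1 (unless it ended earlier) and is treatment-emergent. The drug is dated to the first of the month.

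**Working it through.** The plan gives no figure on this point, so there is none to reproduce. The check applies the rules to calendar dates.

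**Example (dates assumed).** First patch 10 March 2016; in Cohort 1, first tablet 42 days earlier, on 28 January 2016. True start 20 March 2016, box not ticked, drug ongoing.

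| Cohort | Missing | Imputed start | Prior | Tablet-phase | Day -1 use |
|---|---|---|---|---|---|
| 2 | day | 1 March | yes | n/a | yes |
| 2 | month | 1 January | yes | n/a | yes |
| 1 | day | 1 March | no | yes | yes |
| 1 | month | 1 January | yes | yes | yes |

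In every row the drug also counts as patch-phase concomitant, because it was used on patch.

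**When it happens.** An on-patch start with the day missing moves before Day 1 only if it lies in the calendar month of Day 1 and Day 1 is not the 1st. With the month missing, the condition is the same calendar year and Day 1 not 1 January. Other partial dates stay on patch. In Cohort 1 a day-missing on-patch start cannot become prior after a full tablet course, since 42 days is longer than any month.

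**Share affected.** Assumptions, not in the documents: Day 1 uniform over the 516 days from 1 February 2015 to 30 June 2016; tablet phase 42 days; true start uniform over patch days 1 to 364; drug ongoing. That gives 516 × 364 = 187,824 combinations, or 516 × 14 = 7,224 for starts in patch days 1 to 14.

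- Day missing, before Day 1. A month of L days contributes L(L − 1)/2. Nine months of 31 days, six of 30, one of 28 and one of 29 give 9 × 465 + 6 × 435 + 378 + 406 = 7,579. 7,579/187,824 = 4.0%.
- Day missing, starts in days 1 to 14. A month contributes 91 + 14(L − 14), which gives 9 × 329 + 6 × 315 + 287 + 301 = 5,439. 5,439/7,224 = 75.3%.
- Month missing, before Day 1. Days left in the year are summed over Day 1 (capped at 364; zero for 1 January): 55,945 for 2015 and 49,774 for 2016, total 105,719. 105,719/187,824 = 56.3%.
- Month missing, starts in days 1 to 14. The exceptions are 91 that cross the year end and 14 with Day 1 on 1 January. (7,224 − 105)/7,224 = 98.5%.
- Month missing, prior in Cohort 1. This needs Day 1 on or after 13 February of the recorded year: 52,003 + 35,306 = 87,309. 87,309/187,824 = 46.5%.

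**Sensitivity to the Day 1 assumption.** With first patch uniform over a year, or over a month of about 30.4 days (mean 15.2 days left):

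- Starts over 364 days: 1 − 182/365 = 50% (month missing) and 15.2/364 = 4% (day missing).
- Starts over the first 42 days: 1 − 21/365 = 94% and 15.2/42 = 36%.

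**The case against.** A reader might infer that the plan understates antiparkinson use on the patch. The documents do not support that. Prior and concomitant labels may overlap, so a backdated drug keeps its patch-phase label. The percentage required by protocol 15.3.6.4 and the overall row in SAP 9.7 do not change. In the week bands the error runs the other way: an earlier imputed start adds use to windows before the true start. Understatement is confined to new use, through the Day -1 row and the non-user subgroup.

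A reader might also infer that the imputed date contradicts the CRF. It need not. SAP 9.7 ties the box to use before taking part in the study, not before first dose. Washout can last 28 days, and antipsychotic and antiparkinson use in it is recorded (SAP 7.2.2), so an unticked drug can truly precede first dose. In Cohort 1 it can truly have begun on tablet; protocol 10.3.3.2 plans for antiparkinson drugs carried from tablet into patch. For such drugs the early date may be right, and the shares above say nothing about them. For antiparkinson drugs in Cohort 2 this carries less weight: the same section bars starting them between screening and first patch.

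The adverse event rule has a different purpose, to lean towards treatment-emergent, so the contrast is not itself an error. Taking the earliest compatible date is a common convention, the summaries are descriptive, and the listings show the unimputed date. All of this stands. It limits the size of the point but does not justify dating an on-treatment start before first dose when a later date fits the record equally well.

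**Conclusion.** The point holds in a limited form and is of low severity. Rules 3 and 4 can place a drug begun on treatment before the first dose when the recorded month or year contains that dose. In Cohort 2 it then becomes prior medication and Day -1 use. In Cohort 1 it becomes tablet-phase and Day -1 use, and prior medication mainly when the month is missing. The figures that can be wrong are the prior and tablet-phase tables, the Day -1 row, the Day -1 non-user subgroup and, upwards, the early patch windows.

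The calculated percentages are shares of partial dates among drugs that truly began on patch, under assumed uniform timing. They are not shares of all medications. The documents do not say how many dates will be partial, so the effect on any table cannot be stated.

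**What to change.** Amend rules 3 and 4 for unticked drugs. If the known month (rule 3) or year (rule 4) is that of the first study-drug dose (first tablet in Cohort 1, first patch in Cohort 2), set the start to that dose date, or to the stop date if earlier. Leave both rules unchanged when the recorded month or year lies wholly before or after. A floor on every unticked date would be wrong: it would overwrite a month recorded as wholly before first dose.

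In the example, both Cohort 2 starts become 10 March, neither prior nor Day -1 use. In Cohort 1 the month-missing start becomes 28 January, no longer prior but still tablet-phase and Day -1 use; the day-missing start stays at 1 March. Cohort 1 antiparkinson drugs whose partial date fits both periods should not all be assigned to patch, because that would turn true tablet-phase starts into new patch use. Instead, repeat the Day -1 non-user summary with their start set to the first patch date, as a sensitivity analysis.

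The cost is a short SAP amendment, a small programming change and one repeated table, with no new data. Two limits remain. A drug truly begun in washout in the first-dose month or year would be dated to first dose. Week bands before the true start can still be overstated.
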